### **5.1.H. Data Collection Strategy**

Blinded research staff will collect data from patient-participants after all assessments (baseline, post-intervention, and post-maintenance follow-ups). Data to be collected include self-reported measures (see Table 10) and an HbA1c level. Participants will receive \$25 for completing the assessment at each time period, for a total of \$75 throughout the course of the study.

**5.1.H.i. Baseline Data Collection and Assessment.** Baseline data collection will occur in person following informed consent at the introductory meeting. A research assistant will be present to distribute the self-reported measures and to answer any questions that participants may have. The self-reported measures will be completed on paper following consent and collected by the research staff. The research staff will review for incomplete measures to guard against missing data. Paper data will be entered by research staff into an Access database for analysis.

Following the introductory meeting, participants will visit the lab to have blood drawn for a baseline HbA1c level. Blinded research staff will coordinate HbA1c collection with PACT team assistance.

Additional verbal baseline measures of functional health literacy, activation and prior exposure to diabetes management resources will be collected by research staff via telephone. These measures will be collected verbally during the randomization call because subjects with limited health literacy may not be able to read or fully comprehend a written measure.

**5.1.H.ii. Data Collection at Follow Up Assessments.** Post-intervention follow up assessments will be targeted for collection at 5-months after the date of randomization, with assessments occurring no earlier than 4 months after randomization and no later than 6 months after randomization. The assessment following the maintenance phase (Figure 3) will be targeted for collection at 10-months after the date of randomization. Self-reported measures at follow up assessments will be collected by central research staff via telephone using a structured data collection tool. To guide completion of the telephone interview, participants will be mailed blank assessment packets for reference. Blinded research staff will be trained to administer questionnaires by telephone at follow-up assessments and to instruct participants on how to accurately respond to questionnaires. A structured guide will steer participants through response options. We have implemented these procedures in previous studies to improve data collection and reduce missing data. Patient assessments will not be audio-recorded during the study.

Study staff, working with PACT clerical staff, will schedule a lab visit for HbA1c within 2 weeks of the target data collection time. When a clinical HbA1c lab value is available within the data collection window, it will be used for the research analysis.

Study staff will also perform chart abstraction of patient-level characteristics and clinical or PACT/facility variables that may account for confounding. The patient-level characteristics will include: weight, body mass index, Deyo comorbidity score, receipt of other related treatments (e.g. diabetes education), and primary care visits in the last 12 months.

**5.1.H.iii. Attrition/Retention Estimates.** Given the benefits of the computerized patient record and our prior experience with VA participants, we expect that rates of missing data for primary outcomes will be <15%. While we may experience a lower adherence with EPIC group sessions, it is reasonable to anticipate having primary outcomes data for  $\geq 85\%$  of participants, as reflected in our sample size and power estimates. To handle missing data, we will conduct sensitivity analyses using tests for data missing completely at random and tests for nonrandom missingness. These analyses will allow us to evaluate whether the reasons for loss to follow-up at the various time periods are related to the observed values of the outcome variables. Additionally, we will plot the data over time to visually assess changes in outcomes from baseline to 1-year and to indicate whether additional terms are needed in the models to account for nonlinearity over time.

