#### **5.5.B. Data Collection Strategy § 5.1.H.**

#### **5.5.C. Study Variables § 5.1.I.**

### **5.6 Data Analysis**

#### **5.6.A. Sample Size Calculation/Sample size determination**

Sample size is calculated according to the estimated intervention effect size at post-intervention. We then estimate power to detect treatment effects at the post-maintenance (10-month) follow-up as well as power to detect treatment differences in linear change across the three time points for a 3-level cluster-randomized trial with repeated assessments. We will adjust models for baseline covariates of study patients. All tests will be two-sided with an alpha of 0.05. In our recent RCT, differences in HbA1c change between EPIC versus enhanced group education indicated medium treatment effects at post-treatment and at 1-year (Cohen's  $d = 0.48$  and  $0.42$ , respectively). A similar trial revealed a treatment difference between a glucose self-monitoring protocol and an active control group in DDS scores that correspond to large effects of treatment at 1-year (all pre-post  $d$ s  $> 0.80$ ). To capture treatment effects for both clinical and patient centered outcomes in this implementation trial, a conservative small-to-medium effect size of  $d = 0.40$  (which is 16.67% smaller than the effect found for HbA1c in the prior trial) was used to calculate sample size. Assuming no intra-class correlation (ICC) within

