PACTs, 100 patients in each treatment arm (i.e., EPIC and EUC) will allow for 80% power to detect small-to-medium effects and 98% power to detect medium effects ( $d = 0.50$ ). To account for the dependency among patients within a PACT, the Design Effect (Deff) was applied, following the approach of Schnurr et al. The sample size was inflated using the formula,  $Deff = 1 + (n-1)\rho$ , where  $n$  is the average number of patients per PACT and  $\rho$  is the ICC for PACTs. In our preliminary work, we identified an ICC for PACTs of 0.0183, an average of 27 eligible patients per PACT, and expect that an average of 12 patients per PACT will participate, which yields  $Deff = 1 + (12-1) * 0.0183 = 1.2013$ . Applying this adjustment, the minimum number of patients in the clustered design is  $100 \times 1.2013 = 120$  in each treatment group. Further adjusting for a maximum of 15% attrition, 142 patients will be recruited for each treatment group (total  $N = 284$ ). Therefore, the minimum number of PACTs to be sampled for this nested analysis is technically 11.8, (i.e.,  $142/12$ ), which will be rounded up to 24 PACTS. This is highly feasible, representing just 32.5% of the total number of PACTs (75) at all study sites. Treatment group effect sizes as small as  $d = .40$  can be detected with 80% power at 1-year given a total of 284 patients (an average of approximately 12 patients randomized to either EPIC or EUC from within 24 PACTs sampled), even after accounting for maximum attrition and estimated dependency within PACTs. A sample size of 284 participants is adequate for repeated measures analyses as well. Optimal design software estimated power to detect treatment group differences in linear change across all three assessments. Prior data indicated a main effect of treatment (EPIC versus enhanced group education) for linear change in HbA1c of 0.20, and between – and within – PACT variance in linear change of 0.018 and 0.206, respectively. These values indicate a small-to-medium between-groups effect size of 0.42. A total of 284 participants allows for 80% power to detect a slightly larger effect size ( $\delta = .53$ ) for repeated measures analyses of linear change over time. Furthermore, there is 98% power to detect a medium effect size of  $\delta = .75$ .

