Specific Aim 2: The distributional nature of all variables will be assessed, and nonparametric tests (e.g., Fisher's Exact Test; Mann-Whitney test), data transformations (e.g., log linear), or other alternate methods (e.g., weighted least squares regressions) will be conducted where appropriate. First, we will compare baseline demographic, clinical, and patient-centered variables (including medication use) between EPIC and EUC with chi-square and independent samples t-tests. Variables with p-values  $< 0.25$  will be included as control variables or propensity scores in subsequent models. We will then compare baseline demographic, clinical, and patient-centered variables between those who complete the study and those who do not using chi-square and independent samples t-tests. Outcome analyses at both post-intervention and post-maintenance will be intention-to-treat and will use the multiple imputation procedures Proc MI and MINANALYZE in SAS Version 9.3 to estimate missing observations. We will evaluate the degree of dependency between patients within a given group session, between patients in a given PACT, and between PACTs within each of the five sites (by examining Intra Class Coefficients). It is likely that significant dependency will exist, and if so, we will accordingly take these into account in analyses (i.e., patients will be nested within PACTs which will in turn be nested within sites). Random regression methods using SAS Proc Mixed will be employed to account for clustering of data.

5.6.C.i. H2 Analyses (Effectiveness) We will employ Analysis of Covariance (ANCOVA) to examine treatment differences in outcomes immediately post-intervention (at 4 months). We will conduct two models: one with HbA1c at post-intervention as the outcome and one with DDS at post-intervention as the outcome. Models will include treatment group (i.e., EPIC versus EUC) as a predictor and respective HbA1c and DDS baseline scores and any demographic,

clinical, or patient-centered variables that differed between the study arms at baseline as covariates. We will calculate treatment effect sizes immediately post-intervention.

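### The missing-data tests cannot reveal dropout that depends on unobserved outcomes, and no missing-not-at-random re-analysis of HbA1c or DDS is specified

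*Combined protocol and SAP*

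**What the plan says.** Section 5.1.H.iii sets the expectation that "we expect that rates of missing data for primary outcomes will be <15" per cent. It then names "sensitivity analyses using tests for data missing completely at random and tests for nonrandom missingness" and says that these will show whether the reasons for loss at each time period are "related to the observed values of the outcome variables". It adds plots of the outcomes over time. It does not define the tests for nonrandom missingness, and it does not say what follows if one is positive.

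Under Specific Aim 2 in section 5.6.C, the outcome analyses at both follow-ups "will be intention-to-treat and will use the multiple imputation procedures Proc MI and MINANALYZE in SAS Version 9.3 to estimate missing observations". No imputation model or missingness assumption is given. The same paragraph compares baseline variables "between those who complete the study and those who do not using chi-square and independent samples t-tests".

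Two other places touch on incomplete data. The growth-curve model in 5.6.C.iii uses all three assessments but is exploratory. Inverse probability weighting appears under Specific Aim 1, for costs only.

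Section 5.1.H.ii says how follow-up outcomes are obtained. Self-report measures, DDS among them, are collected by telephone by blinded staff. For HbA1c, a clinical laboratory value inside the window is used when there is one.

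**The concern.** A missing-data sensitivity analysis should show how the treatment effect moves when the missingness assumption changes. The tests in 5.1.H.iii do not do that. A relation between dropout and observed values bears on whether data are missing completely at random or at random. It says nothing about dependence on the values that were not collected, which is what defines MNAR. Whatever the tests show, they leave one estimate of the effect, resting on one assumption.

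Proc MI, with nothing further specified, imputes under MAR. That is an inference, since 5.6.C does not state the assumption, but it is the natural reading.

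Patients know their arm (5.1.E.iii and 5.1.E.iv), and the arms differ in what they ask: six group and six individual sessions in EPIC, against a referral, a packet and a letter in EUC. Loss of outcome data that depends on arm and response is therefore possible. If patients who do poorly in EPIC are the ones who stop answering, MAR imputation fills their values too favourably and the benefit of EPIC is overstated. DDS is the more exposed outcome, because a missed telephone interview has no substitute.

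**Working it through.** **Inputs from 5.6.A.** d = 0.40; 80% power; 100 per arm before adjustment; ICC 0.0183 with 12 patients per PACT; "All tests will be two-sided with an alpha of 0.05"; and "Further adjusting for a maximum of 15% attrition, 142 patients will be recruited for each treatment group".

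**Reproducing the plan's sample size.**
- A two-sample calculation at d = 0.40 gives 99 per arm (99.1 with the t distribution), in line with 100.
- Deff = 1 + 11 × 0.0183 = 1.2013, so 100 × 1.2013 = 120.
- 120 / 0.85 = 141.2, so 142 per arm and 284 in total. The figure reproduces.
- Effective n per arm at 15% missing = 142 × 0.85 / 1.2013 = 100.5, and power is 80.9%.

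**Bias from a shift (assumed, not from the documents).** Suppose missing EPIC patients are worse than MAR predicts by s SD and EUC dropouts match MAR. Then bias = share missing in EPIC × s. With 15% and s = 0.5: 0.15 × 0.5 = 0.075 SD, and 0.075 / 0.40 = 19%. Equal shifts with equal missingness in both arms cancel.

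**Power under a shift.** With a true d of 0.40 and 15% missing in both arms, EPIC-only shifts of 0.25, 0.5 and 1.0 SD leave effects of 0.363, 0.325 and 0.250. Power falls from 81% to 73%, 63% and 43%.

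**Tipping points for an observed d of 0.40.** SE = sqrt(1/n1 + 1/n2) on effective sizes; margin = 0.40 − 1.96 × SE; tipping shift = margin / share missing in EPIC. The 25% rate is an assumption.

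| Missing EPIC / EUC | Effective n | SE | Margin | Tipping shift |
|---|---|---|---|---|
| 15% / 15% | 100.5 / 100.5 | 0.141 | 0.123 | 0.82 SD |
| 25% / 15% | 88.7 / 100.5 | 0.146 | 0.114 | 0.46 SD |
| 25% / 25% | 88.7 / 88.7 | 0.150 | 0.106 | 0.42 SD |

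With equal missingness of 5%, 10%, 20% and 30%, the tipping shifts are 2.77, 1.31, 0.57 and 0.32 SD. For a smaller observed effect of 0.30 at 15% missing, the margin is 0.30 − 0.2765 = 0.0235 and the tipping shift is 0.0235 / 0.15 = 0.16 SD.

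These SEs are unadjusted, as in the plan's own sample size. Precision gained from baseline adjustment would raise the tipping shifts.

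**What a test on observed data can see.** Simulation of 4,000 trials per scenario: 142 per arm, about 15% missing, assumed baseline–outcome correlation 0.5, logistic dropout slope of 1 per SD, no PACT clustering, ANCOVA on observed data. The check is a t-test of baseline values in dropouts against completers.
- Dropout driven by observed baseline: the test rejects in 99.9% of trials, and the estimated effect is 0.399 against a true 0.40.
- EPIC dropout driven by the part of the outcome unrelated to baseline: the test rejects in 5.7% (nominal 5%), and the estimated effect is 0.515 against 0.40.
- The same mechanism with no true effect: the estimate is 0.115 and the false-positive rate is 17.9% instead of 5%.

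The second mechanism is the hardest case for the test. Dropout driven by the whole outcome would leave some trace in baseline values.

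**The case against.** The tests are not useless. Baseline HbA1c and DDS are observed, and so are 4-month values for patients lost before 10 months. Dropout that depends on these can be found, as the first simulation shows. A reader might infer that the tests miss all outcome-dependent dropout; the documents do not support that. The blind spot is dependence on unobserved values.

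A reader might also infer that nonrandom missingness was ignored. It is named. What is lacking is a definition of the tests and any re-estimation of the effect.

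A third tempting step is from EPIC's session load to differential loss of outcomes. Section 5.1.H.iii separates the two: it allows for lower session attendance and still expects primary outcome data for at least 85%. Telephone follow-up, clinical HbA1c values and payment of $25 per assessment for participants in either arm support that. Someone who stops attending can still supply both outcomes. EUC also carries some contact, through the RN Care Manager referral and encouragement to schedule routine visits, and some EPIC individual sessions may be by telephone. Differential loss is therefore possible, not established.

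Finally, delta adjustment is one MNAR method among several, and the documents supply no range for the shift. That is fair. The need is for a prespecified MNAR analysis; the particular form is a choice.

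None of this supplies an alternative estimate of the HbA1c or DDS effect.

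**Conclusion.** The concern holds in a limited form. The planned tests cannot reveal dropout that depends on unobserved outcomes, they produce no alternative treatment effect, and no section re-estimates HbA1c or DDS under MNAR. That the imputation rests on MAR is inferred from the lack of any other specification.

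A reader might infer that the intention-to-treat result is fragile as planned. The figures do not show that: with at most 15% missing, an observed d of 0.40 withstands an EPIC-only shift of about 0.8 SD. Protection falls quickly with higher attrition (about 0.46 SD at 25% in EPIC and 15% in EUC, 0.42 SD at 25% in both) and with smaller effects (about 0.16 SD for d = 0.30 at 15%). All shifts, and the 25% rate, are illustrative assumptions, and EUC dropouts are taken to match MAR. The concern is stronger for DDS than for HbA1c. This is a worthwhile, low-cost improvement and not a flaw that undermines the design.

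**What to change.** In 5.1.H.iii and 5.6.C:

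1. State the imputation model, including at least arm and the baseline and 4-month outcomes, and state that the main analysis assumes MAR.
2. Add a delta-adjusted (tipping-point) multiple imputation for HbA1c and DDS at both follow-ups. Shift the imputed values in the unfavourable direction, in EPIC alone and in both arms, over a prespecified range, for example 0 to 1 SD, with the SD defined in advance.
3. Report the shift at which each H2 and H3 conclusion changes.
4. Keep the missingness tests and the completer comparison, labelled as descriptive.

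Sample size and data collection do not change. The cost is a little extra programming on imputations already planned, and possibly a less favourable statement about robustness.

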### **5.1.I. Study Variables**

**5.1.I.a. Screening Interview.** The screening interview will be conducted over the phone and will identify exclusionary variables by self-report that would render participation in a group clinic inappropriate: 1. Substantial hearing or vision loss, such that participation with the materials and group exercises would not be possible. 2. Transportation or availability barriers, such that would prevent the participant from presenting in person on a regular basis. 3. Unwillingness to discuss their health and health care in a peer-group setting. 4. Cognitive functioning. Cognitive functioning will be assessed using a six-item screening tool that has been validated for telephone use. 5. Current active substance abuse. We will administer modules from the MINI, a short structured interview used to identify mental health conditions including substance abuse according to DSM-IV. It is appropriate for telephone screening (Attachment 9 and 10).

**5.1.I.b. Primary Outcomes.** **1. Diabetes Control Measure.** HbA1c is an established measure of diabetes control and a strong predictor of subsequent health outcomes related to diabetes. There is consensus that levels  $>7\%$  should be treated because of their association with both cardiovascular risk and microvascular end-organ damage (e.g., kidney failure). Our eligibility criteria of HbA1c of  $\geq 8\%$  at baseline allows for detection of a clinically significant change without limiting enrollment to only those with very poor control or other selective groups. **2. Diabetes-related Distress Scale (DDS).** DDS, a 17-item instrument that assesses psychological burden specific to diabetes care (see Attachments 7, 8, and 11), has high internal consistency, reliability ( $\alpha = 0.93$ ) and validity with self-care behaviors ( $r = .30, P < .001$ ) and physical activity ( $r = .13, P < .01$ ). DDS scores correlate with HbA1c levels and are a robust measure of other clinically significant diabetes self-management endpoints. Phase 2 study measures and the data collection timeline are outlined in Table 10.

**5.1.I.c. Baseline Covariates.** **1. Patient-Level Characteristics (Self-report):** We will collect date of birth, gender, race, education, living situation [alone or not], social support, VA

copay status, employment status, and prior receipt of related treatments. **2. Patient-Level characteristics** will be obtained by chart review and from the Corporate Data Warehouse. (Chart review) A trained research assistant will conduct a structured chart review to extract data on relevant weight, body mass index, Deyo comorbidity score, receipt of other related treatments (e.g., diabetes education), and primary care visits in the prior 12 months. (Corporate Data Warehouse) We will ascertain adherence to refills of prescribed medications (medication possession ratios for all diabetic medications including insulin) for enrolled patients. **3. Health System / Clinic Characteristics:** We will collect facility, primary care, and PACT characteristics from the Corporate Data Warehouse to account for potential confounding. **4. Patient self-management knowledge and understanding of diabetes** will be assessed using a validated 13-item measure that has demonstrated adequate internal consistency ( $\alpha = 0.68$ ) and correlation with HbA1c values. **5. Patient-reported measures:** We will assess levels of FHL and patient activation at baseline. These measures will be collected verbally during the randomization call because subjects with limited health literacy may not be able to read or fully comprehend a written measure. These measures will be reported to the EPIC interventionists and blinded for those in the EUC arm. **A) Functional Health Literacy:** We will use three questions developed by Chew et al and the eight question SKILLD survey, developed by Rothman et al (see Attachment 12). They have been validated across multiple VA samples to correlate with expanded measures of health literacy including the Rapid Estimate of Adult Literacy in Medicine (REALM) and Test of Functional Health Literacy in Adults, short form (S-TOFLA). These items require less than three minutes to complete and have been validated among patients with diabetes. **B) Patient Activation:** The Patient Activation Measure (PAM) assesses patients' skill, confidence, and knowledge in managing issues related to their healthcare (see Attachment 12). This 13 item scale can be completed in less than ten minutes. PAM scores have been associated with diabetes outcomes in primary care samples.

**5.1.1.d. Predictors and Mediators of Intervention Outcomes.** **1. Self-Efficacy for Diabetes Self-Management** is an eight-item instrument (Cronbach's  $\alpha = 0.83$ ) that measures confidence in performing specific diabetes management tasks with a per item mean of  $6.87 \pm 1.8$ . It has demonstrated correlation with HbA1c levels. **2. Medication Adherence.** We will measure adherence to prescribed diabetes medications using pharmacy refill records from the Corporate Data Warehouse. For each identified medication we will calculate medication possession ratios and refill gaps (See Attachment 7, 8, and 11). We will also capture by self-report the Morisky Medication Adherence scale. This scale allows for identification of patients at highest risk for poor outcomes due to non-adherence as well as recognition of barriers to medication compliance. Responses are scored using a dichotomous scale (yes = 0; no = 1) with higher scores reflecting better medication adherence. The scale has been shown to have good concurrent and predictive validity as well as high internal consistency, indicating good reliability (Cronbach's  $\alpha = 0.83$ ). **3. Depression Symptoms.** The PHQ-8 is an eight-item instrument (Cronbach's  $\alpha = 0.83$ ) that measures depressive symptoms. **4. Exercise.** The Lorig Exercise scale is a six item instrument that measures exercise behavior during a typical week. No Internal reliability reported; test re-test for stretching and strengthening  $r = .56$ ; test-retest for aerobic exercise  $r = .72$ . **5. Diet.** The Diet scale is a ten-item (Cronbach's  $\alpha = 0.73$ ) instrument developed as part of the Diabetes Self-Care Activities survey, a 25- item instrument that measures perceived adherence to diabetes self-care recommendations. **6. Goal-Setting Evaluation Tool for diabetes (GET-D)** is an objective rater scale developed and validated for scoring the quality of goals and action plans articulated by patients in our prior goal-setting

studies (see Attachment 7, 8, and 11). 5. Treatment Fidelity. We will also use a measure, described in § 5.1.F.iii., to objectively rate staff member fidelity to the intervention.

Table 10. Measures	Screen	Baseline	4 M	10 M	Measure	Baseline	4 M	10 M
Screening protocol	X				Intervention Mediators and Moderators			
Primary outcome variables					PHQ-8 Diabetes Self-Care Self-Efficacy	X	X	X
HbA1c levels	X	X	X	X	Diet/Exercise	X	X	X
Diabetes Distress Scale		X	X	X	Pharmacy refills (database)	X	X	X
Baseline Covariates					Goal-Setting Evaluation Tool	X	X	X
Patient Activation Measure		X	X	X	Attendance in group visits		X	X
Functional Health Literacy measure		X			Post-intervention Implementation variables			
The Spoken Knowledge in Low Literacy in Diabetes (SKILLD) Knowledge Assessment Scale		X			Patient exit interviews (Attachment 7)		X	
Patient Socio-demographics		X			Clinician exit interviews (Attachment 13)			X
Baseline clinical characteristics		X			Summative implementation variables			
PACT and facility characteristics		X			Reach and Adoption measures	X	X	X
Patient knowledge & understanding of DM					Fidelity measures	X	X	X
EQ-5D		X	X	X				
		X	X	X				

